3.8.4 Handling of missing values/censoring/discontinuations

All missing data will simply be described as missing until not specified on appropriate tables/listings in particular for patients who will not have reached Tanner Stage V or the age of 16 years (for females) or the age of 17 years (for males) at the end of the CRAD001M2305 study or at the end of the TOSCA registry using the FAS Puberty or Height, BMI analysis using the FAS population.

3.9 Secondary objective

The following secondary objectives will be described: the long term-safety, the age at Tanner Stage II-V, the age at thelarche and menarche for females, the age at adrenarche for males and the TAND Checklist responses.

Additionally an indirect comparison of CRAD001M2305 and TOSCA will be performed to compare the height, BMI and sexual development (using Tanner Stages) if the number of patients in the studies are sufficient.

The secondary safety objective of the study will be based mainly on the frequency of AEs during the follow-up period of the CRAD001M2305 study.

All safety data will be listed.

3.9.1 Adverse events

AEs which will be counted for a specific period are those which are **treatment-emergent**. These events are those with an onset on or after the start of the treatment period, or which were present prior to the start of the treatment period but increased in severity or developed into SAEs after the start of the treatment period.

AEs collected during the CRAD001M2305 study will be described. All listings and tables will be presented for all CRAD001M2305 patients using the Safety Set.

For CRAD001M2305 patients, using the Safety Set, the overall observation period will be divided into two mutually exclusive segments:

1. everolimus exposure period: from day of first commercial dose received in the CRAD001M2305 study to 30 days after the last commercial dose received in the CRAD001M2305 study.
2. post-everolimus exposure period:
 - starting at day 30+1 after the last commercial dose received in the CRAD001M2305 study
 - or
 - starting at the enrollment date for patients who will stop everolimus in CRAD001M2301 and who will not start commercial everolimus.

The safety summary tables will include only assessments collected during the everolimus exposure period. The safety listings will include all assessments, with those collected during the post-everolimus exposure period being flagged.

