## Development

In animal studies it was shown that signaling through mTOR was at least partially involved in the control of puberty onset. Chronic blockade of mTOR by rapamycin had a strong inhibitory impact on puberty onset in female rats. Preliminary results suggested that also male rat puberty is sensitive to mTOR inactivation. Toxicology studies performed with everolimus demonstrate that treatment with everolimus may be associated with decreased weight in rodent pups and a delay in descent of testes in male pups.

Additionally, the safety profile of everolimus in Study [CRAD001M2301] was consistent with that observed in the phase II study [CRAD001C2485] in patients with TSC with the exception of three cases of secondary amenorrhea. Secondary amenorrhea is thought to be an indicator of end-stage ovarian dysfunction. It has been speculated that this finding may be a consequence of TSC-related-mTOR over-expression or mTOR inhibition.

Due to these preclinical and clinical findings further investigation of possible effects of long-term everolimus treatment on the onset of puberty and development of TSC patients is imperative. This study is designed to address these questions. The timing of puberty onset and development through the different stages to full maturation will be monitored by assessment of Tanner Stage and if achieved prior to study completion timing of menarche and thelarche (females) or adrenarche (males).

In addition, many of the patients who will be enrolled in this study have previously received and will be taking antiepileptic drugs (or enzyme-inducing antiepileptic drugs [EIAED]). While in general it is not thought that antiepileptic drugs impact ultimate height, the studies have not been comprehensive (Macardle et al 1986). Additionally, some antiepileptic drugs (e.g., valproic acid, topiramate) may affect weight in the peri-pubertal period (Novak et al 1999). As a consequence, this study may generate some observations about the dual exposure of patients to antiepileptic drugs and everolimus.

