### **7.2.2.3 Endocrine testing**

A blood sample for analysis of luteinizing hormone (LH), follicular stimulating hormone (FSH), and estrogen (females) or total testosterone (males) will be collected on day 1, annually, and at end of study for endocrine assessment at a local laboratory for all patients, starting at age 10 until study participation is ended. In the event that amenorrhea is reported in between scheduled assessments, hormone evaluations should be completed at that time.

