2.3.2 Safety Set

The Safety Set (SS) will include all patients enrolled in the CRAD001M2305 study who have at least one-post CRAD001M2305 baseline safety assessment. It should be noted that all patients enrolled in the CRAD001M2305 study have been exposed to everolimus in the parent study CRAD001M2301 (and may or may not continue receiving commercial everolimus while on CRAD001M2305).

The safety set will be the population used in the assessments of safety, such as adverse events (AEs) and everolimus exposure.

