3.1 General presentation of descriptive summaries

Qualitative data (e.g., gender, race, etc.) will be summarized by appropriate descriptive statistics (i.e. frequencies and percentages); a missing category will be included as applicable. Percentages will be calculated using the number of patients in the relevant population or subgroup as the denominator.

Quantitative data (e.g., age, body weight, etc.) will be summarized by appropriate descriptive statistics (i.e. mean, standard deviation, median, 25th and 75th percentiles, minimum, and maximum).

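### Secondary amenorrhoea, one of the findings cited to justify the study, has no analysis of its own; it is summarised over the whole Safety Set and only within the everolimus exposure period

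*SAP*

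**What the plan says.** Protocol 1.1.3 (Development) reports that the safety profile in the parent study matched that of the earlier phase II study "with the exception of three cases of secondary amenorrhea", and describes the event as a possible sign of end-stage ovarian dysfunction. It then draws the animal and clinical results together: "Due to these preclinical and clinical findings further investigation of possible effects of long-term everolimus treatment" on onset of puberty and development is called for.

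Protocol 7.2.2.3 attaches a procedure to the event: "In the event that amenorrhea is reported in between scheduled assessments, hormone evaluations should be completed at that time".

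No objective or endpoint names it. The menstrual outputs in SAP 3.9.2 are age at menarche, and absence of menarche as part of potential delayed puberty. Neither captures periods that stop after they have begun.

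The event is therefore handled by the adverse event rules:

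- **Population.** SAP 3.9.1: "All listings and tables will be presented for all CRAD001M2305 patients using the Safety Set". SAP 2.3.2 restricts that set by neither sex nor menarche: "The Safety Set (SS) will include all patients enrolled in the CRAD001M2305 study who have at least one-post CRAD001M2305 baseline safety assessment".
- **Denominator.** SAP 3.1: "Percentages will be calculated using the number of patients in the relevant population or subgroup as the denominator". No subgroup is defined for adverse events.
- **Period.** SAP 3.9.1: "The safety summary tables will include only assessments collected during the everolimus exposure period", which runs from the first commercial dose to 30 days after the last. For later events, "The safety listings will include all assessments, with those collected during the post-everolimus exposure period being flagged".
- **Special interest groupings.** SAP 3.9.1.5 plans tables by safety topic, on treatment only. No topic is named.

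**The concern.** Only a girl who has reached menarche can have secondary amenorrhoea. A percentage of all Safety Set patients divides by boys and by girls not yet at risk, so it is lower than the risk in those who can have the event.

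The numerator and denominator also differ in coverage. A patient who never starts commercial everolimus falls wholly in the post-exposure period. She stays in the Safety Set denominator, but no event of hers can enter the summary table.

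The SAP already applies the right principle elsewhere: SAP 3.9.2 gives rates of potential delayed puberty by sex, among patients at risk, with 95% confidence intervals.

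Two related gaps bear on the same event. SAP 3.9.1 limits the summaries to treatment-emergent events, whereas SAP 3.9.1.3 also says that they include events ongoing at enrolment. Amenorrhoea carried over from the parent study would be treated differently under the two rules unless it worsened or became serious. Separately, a hormone sample taken because of amenorrhoea can be selected into the routine endocrine summaries, which are a primary endpoint.

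At stake is whether a reader of the tables sees a fair rate for an event that the protocol itself singles out.

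**Working it through.** **Inputs.** N = 15 enrolled (SAP 4.2). The number at risk, m, is not given in either document. I assume that 20% to 50% of the 15 are girls past menarche and take m = 3, 5 and 8. Intervals are exact binomial (Clopper-Pearson), as SAP 2.4.2.2 prescribes for percentage rates.

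**Reproducing the SAP's own figure.** The table in SAP 4.2 gives 1 of 15 as 0.07 (0.00, 0.32). Recomputed: 1/15 = 0.067 (0.002, 0.319). It agrees after rounding.

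**One case.** The Safety Set rate is 1/15, the at-risk rate is 1/m, and the understatement is (1/m)/(1/15) = 15/m.

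| At risk, m | Safety Set rate (95% CI) | At-risk rate (95% CI) | Factor 15/m |
|---|---|---|---|
| 3 | 6.7% (0.2 to 31.9%) | 33.3% (0.8 to 90.6%) | 5.0 |
| 5 | 6.7% (0.2 to 31.9%) | 20.0% (0.5 to 71.6%) | 3.0 |
| 8 | 6.7% (0.2 to 31.9%) | 12.5% (0.3 to 52.7%) | 1.9 |

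**No cases.** The upper 95% limit is 1 − 0.025^(1/n). On n = 15 it is 1 − 0.782 = 21.8%. On n = 5 it is 1 − 0.478 = 52.2%. On n = 3 and n = 8 it is 70.8% and 36.9%. An empty row therefore looks more reassuring on the Safety Set than the data allow.

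**Effect of the period rule.** Suppose two cases, one of them a new onset in the post-exposure period, and m = 5. The summary table shows 1/15 = 6.7%; the count over all follow-up among those at risk is 2/5 = 40.0%. Of this six-fold gap, a factor of 3 comes from the denominator and a factor of 2 from the period.

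**Hormone samples.** Under SAP 2.1.6.1 the windows are centred on each year since the start of everolimus, and the assessment nearest the planned day is used. Protocol 4.1 times annual visits from enrolment in the follow-up study, so a scheduled sample can lie well away from the window centre. The rule does not require that the chosen sample come from a scheduled visit, so one triggered by amenorrhoea can replace the routine one. How often this would happen cannot be computed from the documents.

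**The case against.** The case against is substantial, and much of it stands.

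- A reader might infer that off-drug cases are dropped from the report. They are not: SAP 3.9.1 lists and flags them, and with 15 patients they can be counted by hand. What is missing is a tabulated count with a number at risk.
- A reader might infer that persistence is hidden. An event that starts on drug and continues off it stays in the tables, since counting depends on onset or worsening, and Protocol 8.1.1 records duration and outcome. Only new onsets outside the exposure period miss the tables; events ongoing at enrolment depend on which SAP rule applies.
- A reader might infer that the study fails to answer the question that prompted it. The documents do not support this. The rationale rests mainly on growth, puberty onset and development, with amenorrhoea as one finding among several, and no objective names it.
- It cannot be said that the event will appear only in general tables. A special interest grouping might include it, although none is named and those tables count on-treatment events only.
- Using the whole Safety Set for preferred-term tables is ordinary practice, and the one-case intervals for 1/15 and 1/5 each contain both point estimates. Inference from such small numbers changes little.
- Adverse events are found by non-directive questioning (Protocol 8.1.1), and no routine menstrual history is described, so a rate per patient-year would imply ascertainment that the study does not have.

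None of this supplies an at-risk denominator or a tabulated count of new onsets outside the exposure period.

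**Conclusion.** The point holds in a limited form. An event that the protocol cites as a reason for the study, and for which it orders hormone testing, has no specified analysis. The adverse event rules give a percentage that is too low for those who can have it and leave new onsets outside the exposure period to flagged listings.

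The understatement equals N divided by the number at risk. It is 5.0- to 1.9-fold if 3 to 8 of the 15 patients are girls past menarche. That range is my assumption; the true factor cannot be derived from the documents. The three cases reported from the 117-patient parent study should not be read as an expected count among 15.

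This is a reporting gap with a cheap remedy. It does not undermine the study's primary analyses.

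**What to change.** 1. **SAP 3.9.2, one descriptive table.** Reported secondary amenorrhoea among girls with recorded menarche: n/N with exact 95% confidence interval for the exposure period, the post-exposure period and overall, stating the number at risk in each. A rate per person-time since menarche is optional and should carry the caveat that events come from non-directive questioning.
2. **SAP 3.9.1 and 3.9.1.3.** Reconcile the two statements of which adverse events enter the summaries, and say how an event ongoing from the parent study is counted.
3. **SAP 2.1.6.1.** Flag hormone samples triggered by amenorrhoea, exclude them from the window selection for the routine endocrine summaries, and list them with the event.

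The cost is SAP wording and one small output. Menarche dates, adverse events and dosing dates are already collected; triggered samples would need to be identified from visit and event dates if they carry no marker. The drawback is a small denominator and wide intervals, which the table should show plainly.

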2.1.3 Treatment day / Study day

For CRAD001M2305 patients, the treatment day 1 will be the date of start of everolimus. The treatment day of an assessment that occurred on or after the start of everolimus will be calculated as (date of assessment) – (date of start of everolimus) + 1. The treatment day of an assessment that occurred before the start of everolimus will be calculated as (date of assessment) – (date of start of everolimus).

For TOSCA patients, since they were not exposed to any mTOR inhibitors on the TOSCA study, the concept of study day will be used. The study day 1 will be the enrollment date. The study day of an assessment that occurred on or after the enrollment date will be calculated as (date of assessment) – (enrollment date) + 1. The study day of an assessment that occurred before the enrollment date will be calculated as (date of assessment) – (enrollment date). Treatment day/ Study day will be displayed in the data listings.

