5.1.4 AE, concomitant medication and other safety assessment date imputation

Every effort will be made to get the missing information on partial dates. However, despite best efforts, some partial dates might still exist in the database. They will be listed as is. If needed in a calculation (e.g. duration), the standard Novartis Oncology imputation rules will be used.

Table 5-2 Imputation of start dates (Adverse events, Concomitant Medications)

Missing Element	Rule
day, month, and year	No imputation will be done for completely missing dates
day, month	If available year = year of study treatment start date then If stop date contains a full date and stop date is earlier than study treatment start date then set start date = 01JanYYYY Else set start date = study treatment start date. If available year > year of study treatment start date then 01JanYYYY If available year < year of study treatment start date then 01JulYYYY
Day	If available month and year = month and year of study treatment start date then If stop date contains a full date and stop date is earlier than study treatment start date then set start date= 01MONYYYY. Else set start date = study treatment start date. If available month and year > month and year of study treatment start date then 01MONYYYY If available month and year < month year of study treatment start date then 15MONYYYY

Table 5-3 Imputation of end dates (Adverse events, Concomitant Medications)

Missing Element	Rule For patients who discontinued study: *=last treatment date plus 30 days not > (death date, cut-off date) For patients still on study: *= last contact date on study
day, month, and year	No imputation will be done for completely missing dates
day, month	If partial end date contains year only, set end date = earliest of 31DecYYYY or end date of the on-treatment period*
day	If partial end date contains month and year, set end date = earliest of last day of the month or end date of the on-treatment period*

Any AEs and ConMeds with partial/missing dates will be displayed as such in the data listings.

Any AEs and ConMeds which are continuing as per data cut-off will be shown as ‘continuing’ rather than the end date provided.

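### The adverse-event periods leave a late starter's days before the first commercial dose unassigned, partial-date imputation has no defined anchor, and two table-inclusion rules conflict

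*SAP*

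**What the plan says.** For the M2305 Safety Set, SAP 3.9.1 states that "the overall observation period will be divided into two mutually exclusive segments". The exposure segment counts "from day of first commercial dose received in the CRAD001M2305 study" and closes 30 days past the final such dose. The post-exposure segment opens on day 31 after the final commercial dose for patients who took one. For the others the rule reads: "starting at the enrollment date for patients who will stop everolimus in CRAD001M2301 and who will not start commercial everolimus". Protocol 10.5.1.1 and the protocol summary define the periods the same way. SAP 3.9.1 adds: "The safety summary tables will include only assessments collected during the everolimus exposure period". Listings hold everything, with post-exposure records flagged.

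SAP 3.9.1.3 gives two rules for the summaries. The first admits only events that started or worsened in the exposure period. The next sentence admits all events ongoing at enrolment and during M2305, up to 30 days after the last everolimus dose.

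For partial start dates, Table 5-2 (SAP 5.1.4) compares the recorded year or month with the study treatment start date. With day and month missing the rule is: "If available year > year of study treatment start date then 01JanYYYY". With only the day missing, a later month is set to its first day. The SAP does not define this reference date. SAP 2.1.1 defines the start of everolimus as the first non-zero M2301 dose, and SAP 2.1.3 says "the treatment day 1 will be the date of start of everolimus".

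**The concern.** Two segments that are said to divide the observation period should between them cover every day of it. If they do not, an event on an uncovered day has no defined place in the tables and carries no post-exposure flag in the listings. The 30-day allowance should also apply to any everolimus dose, whichever study supplied it.

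The date rule raises a separate problem. Table 5-2 moves an ambiguous onset to the treatment start when both fall in the same year or month, so the event counts as emergent. If the reference date lies years before M2305, that branch never applies to M2305 events. An on-drug event with a partial date can then be placed before the first commercial dose.

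SAP 3.9 rests the secondary safety objective mainly on adverse-event frequency during M2305 follow-up, so these rules decide what the main safety tables count.

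**Working it through.** The plan gives no figure to reproduce. The check applies its date rules directly.

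**Coverage of the segments.** Take invented dates: last M2301 dose 5 January 2015, enrolment 15 January 2015, first commercial dose 10 March 2015, M2301 start in an earlier year.

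| Onset as recorded | Date used | Segment under SAP 3.9.1 |
|---|---|---|
| 20 Jan 2015 | as recorded | neither, though 15 days after an M2301 dose |
| 20 Feb 2015 | as recorded | neither |
| 20 Mar 2015 | as recorded | exposure |
| Mar 2015 (M2301 anchor) | 1 Mar 2015 | neither |
| 2015 (M2301 anchor) | 1 Jan 2015 | neither, and before enrolment |
| Mar 2015 (first commercial dose as anchor) | 10 Mar 2015 | exposure |

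If the same patient never takes commercial drug, 20 January is post-exposure.

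**Size of the M2301 tail inside M2305.** If enrolment is d days after the last M2301 dose, the part of the 30-day window remaining after enrolment is max(0, 30 − d). This gives 30, 20, 10 and 0 days for d = 0, 10, 20 and 30, and 0 for d = 183.

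**Partial dates.** Assumptions: the M2301 start is in an earlier year, enrolment is on the day of the first commercial dose, that dose may fall on any of the 365 days of a non-leap year, and true onset is equally likely on each day from that dose to the end of the month or year.

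- Day missing: a month of n days gives n(n+1)/2 dose–onset pairs, so the total is 7×496 + 4×465 + 406 = 5,738. The imputed first of the month is on or after the dose only if dosing began on that day, which accounts for 7×31 + 4×30 + 28 = 365 pairs. Misplaced: (5,738 − 365)/5,738 = 5,373/5,738 = 93.6%.
- Day and month missing: the total is 365×366/2 = 66,795 pairs. Only a 1 January start is placed correctly, which accounts for 365 pairs. Misplaced: 66,430/66,795 = 99.5%.
- With the first commercial dose as anchor, both figures are 0%, because the same-month and same-year branches set the onset to that dose.

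**Inclusion rules side by side.** For the fully dated gap events (20 January and 20 February), the first rule of 3.9.1.3 and the restriction in 3.9.1 exclude both from the tables. The second rule of 3.9.1.3 includes both, since they arise during M2305 before the last everolimus dose. Two programmers could produce different tables from the same data.

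**Effect on a row.** SAP 4.2 works with 15 patients. If all are in the Safety Set, one patient is 1/15 = 6.7 percentage points.

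**The case against.** The strongest reply is that SAP 3.9.1.3 already tabulates gap events. Its second rule was rewritten in the 2024 amendment, and it refers to everolimus without limiting it to commercial supply. A reader might infer from 3.9.1 alone that these events are lost from every summary table. The documents do not support that, because the second rule would keep them. The reply does not settle the matter, however: the narrower rule stands in the preceding sentence and in 3.9.1. SAP 2.1.2 also takes the last administration date from the M2305 prescription record, so the 30-day limit is unclear for a patient who took only M2301 drug.

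Other parts of the reply stand:

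- A reader might extend the hole back to the last M2301 dose and size it by the 6-month enrolment window. Protocol 8.1.1 counts events in M2305 only after consent and transfers ongoing M2301 events, so the hole runs from enrolment. A longer interval also shrinks the 30-day overlap.
- Gap days are not all on drug. By the SAP's own convention, only those within 30 days of an M2301 dose count as exposed. A patient already on commercial drug at enrolment arguably has no gap, and protocol 2.1 expects most patients to continue treatment.
- Reading the Table 5-2 reference date as the first M2301 dose is an inference. SAP 2.2 sends partial-date detail to programming specifications that are not among these documents.
- Events are sought every 3 months (protocol 4.1), so year-only dates should be uncommon. An event that later worsens or becomes serious is still emergent under 3.9.1.

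**Conclusion.** The point holds, limited to M2305 time from enrolment, and should be repaired before the final tables are programmed. Three things are established from the text: late starters' days before the first commercial dose have no segment; the 30-day tail is given to commercial doses but not to the last M2301 dose in patients who never start commercial drug; and 3.9.1.3 contradicts itself. The partial-date problem is conditional on the M2301 anchor, which is the only treatment start the SAP defines. Under that reading and the uniform-onset assumptions, 93.6% or 99.5% of the affected on-drug onsets are placed before the first commercial dose. These percentages apply only to partial dates in the month or year of that dose.

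The number of patients affected is unknown, because the documents give neither enrolment-to-first-dose intervals nor counts of partial dates. The 6.7 points is the weight of one patient among 15, not an estimate of bias. A reader might conclude that adverse-event incidence is biased low overall. That does not follow, since the outcome depends on which inclusion rule is programmed, and leaving out events that are truly off drug does not lower on-drug incidence. All events remain in the listings.

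**What to change.** (a) In SAP 3.9.1, assign every day from M2305 enrolment to a segment. Count days within 30 days after any everolimus dose, M2301 or commercial, as exposure. Make the remaining days before the first commercial dose a separate, flagged off-drug segment.

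(b) In Table 5-2, define the reference date for M2305 events as the first commercial dose in M2305, or enrolment if the patient is then already on drug or within 30 days of the last M2301 dose. A patient with an M2301 tail at enrolment and a later commercial start has two exposure starts; use the one lying in the recorded month or year, and the earlier if both do. Keep the existing exception for a complete stop date before the reference date.

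(c) In SAP 3.9.1.3, keep one inclusion rule and align it with 3.9.1. Table 2-2 marks M2301 as a source for adverse events while 3.9.1 describes events collected in M2305, so say there what M2301 contributes.

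The cost is SAP wording and date derivations. The pooled exposure analysis already needs the M2301 and commercial dosing dates, so no new data are required. Because protocol 10.5.1.1 has the same two segments, record the change in SAP section 4.

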### **10.5.1.2 Adverse events (AEs)**

Summary tables for adverse events (AEs) have to include only AEs that started or worsened during the everolimus exposure period, the treatment-emergent AEs. However, all safety data will be listed and those collected during the post-everolimus exposure period are to be flagged.

The incidence of treatment-emergent adverse events (new or worsening from baseline) will be summarized by system organ class and or preferred term, severity (based on CTCAE grades), type of adverse event, relation to everolimus treatment and by year since the enrollment date.

The prevalence over time of treatment-emergent adverse events will be described by system organ class and or preferred term.

Deaths reportable as SAEs and non-fatal serious adverse events will be listed by patient and tabulated by type of adverse event.

Clinically notable AEs (CNAE) will be considered. Such categories consist of one or more well-defined safety events which are similar in nature and for which there is a specific clinical interest in connection with everolimus.

For each CNAE, number and percentage of patients with at least one event part of the CNAE will be reported by categories regrouping the relevant preferred terms, as appropriate.

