3.9.1.3 General rules for AE Reporting

Summary tables for AEs have to include only AEs that started or worsened during the everolimus exposure period (treatment-emergent AEs). AE summaries will include all AEs ongoing at the time of enrollment and during the Study (CRAD001M2305) and no later than 30 days after the last dose of everolimus. AEs ongoing at the time of enrollment (CRAD001M2305) and during the study will be listed, and AEs starting later than 30 days after the last dose of everolimus will be specifically flagged.

AEs will be summarized by presenting the number and percentage of patients having at least one AE, and having at least one AE in each body system/primary system organ class (SOC_TXT), and for each preferred term (PT_TXT) using MedDRA coding. A patient with multiple occurrences of an AE will be counted only once in the AE category.

Separate AE summaries will be presented by primary system organ class (SOC), PT, and maximum CTC grade (AEVGRD1C). A patient with multiple CTC grades for an AE will be summarized under the maximum CTC grade recorded for the event.

The frequency of CTC grade 3 and 4 AEs will be summarized separately.

Any information collected (e.g., CTC grades, relationship to study drug, action taken) will be listed as appropriate.

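### The AE summary tables cover only the everolimus exposure period, so adverse events in off-drug follow-up are listed but get no planned count or percentage

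*SAP*

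**What the plan says.** SAP 3.9 describes the secondary safety objective as "based mainly on the frequency of AEs during the follow-up period of the CRAD001M2305 study".

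SAP 3.9.1 splits M2305 observation into two segments:

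- The everolimus exposure period runs "from day of first commercial dose received in the CRAD001M2305 study to 30 days after the last commercial dose".
- The post-everolimus period begins on the day after that window closes, or "starting at the enrollment date for patients who will stop everolimus in CRAD001M2301 and who will not start commercial everolimus".

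The same section fixes what is reported from each. For tables: "The safety summary tables will include only assessments collected during the everolimus exposure period". For listings: "The safety listings will include all assessments, with those collected during the post-everolimus exposure period being flagged". It names the Safety Set as the population for all AE tables and listings.

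Protocol 10.5.1.2 sets the same limit. Its AE summary tables take only events that began or worsened in the exposure period. All safety data are listed, and "those collected during the post-everolimus exposure period are to be flagged".

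**The concern.** The objective is a frequency during follow-up, and part of that follow-up is off drug by design. A flagged listing is not a frequency: it has no count, percentage or denominator. Secondary amenorrhoea is a fair example. Protocol 1.1.3 cites three cases in the parent study among the reasons for further investigation. If it arose more than 30 days after the last commercial dose, or in a patient who never took commercial drug, it would enter no AE table.

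This matters because the study is a post-authorisation safety study that includes past users, and protocol 2.2 asks about previous as well as ongoing treatment. As specified, the tabulated AE frequency describes on-drug time only, and it is diluted by patients who had no on-drug time in M2305.

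**Working it through.** The plan gives no figure for this point, so there is none to reproduce. The check compares the rules and then does one piece of arithmetic on the denominator.

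**1. Does another output count off-drug AEs?**

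| Output | Window stated |
|---|---|
| All safety summary tables (SAP 3.9.1) | exposure period only |
| AE summaries, general rule (SAP 3.9.1.3, first sentence) | began or worsened in the exposure period |
| AE summaries, second rule (SAP 3.9.1.3, second sentence) | adds AEs ongoing at enrollment, but still ends 30 days after the last dose |
| AEs of special interest (SAP 3.9.1.5) | on-treatment period |
| Registry AE and SAE tables (SAP 3.9.1.6) | treatment-emergent |
| Deaths table (SAP 3.9.1.4), death counts (SAP 3.9.1.6) | none of their own |
| Death and SAE tabulation (protocol 10.5.1.2) | none of its own |

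No planned AE table is built for the post-everolimus segment. For deaths and SAEs the text is unclear: some outputs state no window, while the general rule in SAP 3.9.1 appears to apply to all of them.

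**2. Will there be off-drug AE data?** Yes. Protocol 2.1 expects some patients to stop everolimus at the end of M2301, though most to continue. Protocol 7.1.3 keeps patients in the study after they stop commercial drug. Protocol 2.2 and 4.1 plan AE collection every 3 months without limiting it to treated patients.

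**3. Do the two segments cover all M2305 time?** No. If a patient enrols off drug and starts commercial everolimus later, the time from enrollment to that first dose is before the exposure period. It is also outside both definitions of the post-everolimus period.

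**4. What happens to the denominator?** Inputs:

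- N = 15, the sample size given in SAP 4.2. I assume all 15 are in the Safety Set.
- k = patients with no commercial dose in M2305. This is not given, so it is varied.
- p = 40%, an assumed true incidence, the same in every patient.

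Under the SAP 3.9.1 rule the k patients cannot contribute an event, yet they remain in the Safety Set. SAP 3.1 divides by the relevant population. So:

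tabulated incidence = p × (N − k) / N

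- k = 0: 40% × 15/15 = 40%
- k = 3: 40% × 12/15 = 32%
- k = 5: 40% × 10/15 = 26.7%

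The highest percentage any such table could show is (N − k)/N, which is 80% for k = 3 and 66.7% for k = 5. If only patients with exposure-period time are counted, k = 3 gives 40% × 12/12 = 40%, and the dilution disappears.

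**The case against.** The case for leaving the plan alone has five parts.

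- **The restriction is deliberate and conventional.** Main AE tables limited to treatment-emergent events are common practice, and the protocol sets the rule itself. This stands. A reader might infer that the SAP departs from the protocol; it does not.
- **The study's main safety outputs are not cut.** A reader might infer that past users have no tabulated safety results at all. The documents do not support that. Height and BMI SDS, Tanner stage, endocrine values, delayed puberty, the age milestones and TAND (SAP 3.8 and 3.9.2) have no 30-day limit. Absent menarche is itself a delayed-puberty criterion. The point is confined to AE tables.
- **The objective may be narrower than it looks.** SAP 3.9 does not say that frequency will be given over all of follow-up. Its wording may only separate M2305 events from parent-study events, and protocol 10.5.1 refers just to AE frequency. This softens the mismatch. It does not remove it, because SAP 3.9.1 defines the second segment and then plans no summary of it.
- **With about 15 patients a listing can be read in full.** This is true, and percentages from a few patients are coarse: with 3 at risk, one patient is 33%. But a listing does not give the number at risk or the patient-years, and a count cannot be interpreted without them.
- **Off-drug ascertainment is weaker.** Protocol 8.2.2 requires only suspected-related SAEs to be reported beyond 30 days after stopping, and protocol 8.1.1 asks for AE monitoring for at least 30 days after the last dose. This stands, and it limits how an off-drug table may be used.

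**Conclusion.** The concern holds for the AE tables. Events in the post-everolimus segment, including all M2305 time of patients who never start commercial drug, have no planned count or percentage, although SAP 3.9 frames the objective as AE frequency during follow-up. These events are not lost, since they are listed and flagged. Nor can it be said that off-drug deaths and SAEs are certainly uncounted: the documents leave that open.

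The size cannot be fixed from the documents, because neither the number of patients off drug nor the off-drug share of follow-up is given. The dilution is zero if every patient takes commercial drug. It takes a 40% incidence to 32% or 26.7% if 3 or 5 of 15 do not. Those figures assume that all 15 are in the Safety Set, that incidence is equal across patients, and that the SAP 3.9.1 window governs. A loose reading of the second sentence in SAP 3.9.1.3 might admit some events ongoing at enrollment in never-restarters, and the two rules need reconciling. The growth and development results do not depend on this point.

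**What to change.** Keep the on-treatment AE tables and make these changes before final database lock:

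1. Use patients with at least one day in the exposure period as the denominator of the on-treatment tables.
2. Add one AE table and one SAE/death table, with counts by SOC and PT, for the post-everolimus period. Show the number of patients at risk and the patient-years.
3. Assign time from enrollment to a later first commercial dose to a named segment.
4. State whether off-drug deaths and SAEs are counted in the existing death and SAE outputs.
5. Footnote the new tables: beyond 30 days after the last dose only suspected-related SAEs must be reported to the sponsor (protocol 8.2.2), and on-drug and off-drug rates should not be compared directly.
6. Record the addition in SAP Section 4.

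The cost is two tables from data already collected and flagged, plus a few sentences of SAP text. The drawbacks are small denominators and less complete off-drug SAE ascertainment. The footnote discloses the second but does not repair it.
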